11.3.2 Statistical Methods

Mean changes from baseline to each post-baseline visits (as defined in Table 1) and final value in continuous laboratory parameters will be summarized with the baseline mean, visit mean, change from baseline mean, standard deviation, minimum value, median, and maximum value.

Laboratory data values will be categorized as low, normal, or high based on normal ranges of the laboratory used in this study. Cross (shift) tables from baseline to the minimum/maximum/final values according to the normal range will be provided for each hematology, clinical chemistry parameter and urinalysis parameters. The shift tables will cross tabulate the frequency and percentage of subjects with baseline values below/within/above the normal range versus minimum/maximum/final values below/within/above the normal range.

Incidence of abnormal laboratory values for hematology, clinical chemistry parameter and urinalysis parameters will be provided.

Scatter plot of Baseline values versus the final values in laboratory parameters will be provided.

11.4 Analysis of Vital Signs and Weight

The following vital signs are measured at the designated study visits in Table1.

- Blood Pressure (Systolic/Diastolic) (mmHg)
- Pulse (bpm)
- Respiratory rate (rpm)
- Body temperature (°C)
- Body Weight (kg)

11.4.1 Statistical Methods

For each vital sign and weight variable, analyses of the mean change from baseline to each post-baseline value will be presented for the Safety Dataset using the descriptive statistics including 95% confidence interval based on standard normal distribution.

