4.3 Sample Size

GPP is designated as the specified rare and intractable disease in Japan and patient number is quite limited. Assuming the Clinical Response rate of adalimumab in GPP is similar to PASI 75 response in plaque psoriasis, 50% to 60% as expected response rate in adalimumab treatment and 10% as a threshold response rate is hypothesized.

A sample size of 6 to 10 provides over 90% power to detect the difference between expected Clinical Response rate (50 to 60%) and threshold response rate (with no medication, 10%) in GPP, using a one sample Chi-square test with 2.5% one-sided significance level. In case of using Fisher's exact test, an exact binomial test with a nominal 0.025 one-sided significance level will have 82% power to detect the difference between the threshold proportion of 10% and the expected proportion of 50%.

Therefore, the target number of subjects is set 10 subjects, taking the study feasibility into consideration.

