6.5 Definition of Missing Data Imputation

The following methods will be used to impute missing values in the efficacy analyses. In general, missing Baseline and safety data will not be imputed. In addition, an observed case analysis will be performed.

Baseline Value is Missing

Subjects will be excluded from analysis of change from baseline if baseline evaluation is missing.

Non-Responder Imputation (NRI)

The NRI approach is used for binary efficacy variables. These variables can take values of 'Achieved' or 'Not Achieved' or may be missing for any reason including discontinuation from study. According to the NRI imputation approach, all missing value will be considered as 'Not Achieved.'

Last Observation Carried Forward (LOCF)

For continuous variables, the following rules will be used for the LOCF approach:

1. Baseline and pre-baseline values will not be used to impute the missing post-baseline values.
2. Missing values after Study Day 1 will be imputed using the latest non-missing values after Day 1 and prior to the missing value. If there are no non-missing values after baseline, then the LOCF value will be missing.

Observed Cases (OC)

Observed case analysis will be performed such that missing values will not be imputed.

Imputation of Missing Dates

For baseline, efficacy, and safety parameters, if the day and/or month are missing, the following conventions will be used to impute the missing dates:

- 01 for missing start day
- End of month for missing end day

- January 1st for missing start month
- December 31st for missing end month

In case of missing or partially missing dosing dates, the dates will not be imputed.

In case of missing or partially missing adverse event start and stop dates, the dates will be imputed by comparing to the first dosing date so that the corresponding adverse events will be made treatment-emergent, whenever possible.

Rounding

Rounding will be performed only for presentation of results. No rounding will be performed before or during computations. The ROUND function of SAS will be used to round results for presentation.

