9.1 Study Drug Exposure

The duration (days) of exposure to study drug will be summarized using the number of subjects treated, mean, standard deviation, minimum, median, and maximum. Duration of exposure is defined the number of days since first dose of study drug through the last dose date plus 14 days. For interim analysis at Week 24, the Week 24 dosing date will be used instead of last dose plus 14 days only for ongoing subjects. In addition, the number and percentage of subjects exposed to study drug will be summarized for the following duration intervals.

1 – 15 days
16 – 29 days
30 – 57 days
58 – 85 days
86 – 113 days
114 – 141 days
142 – 169 days
170 – 197 days
198 – 225 days
226 – 253 days
254 – 281 days
282 – 309 days
310 – 337 days
338 – 365 days
> 365 days

Exposure to study drug (total patient years) will be summarized.

Cumulative Dose (mg)

Cumulative dose is derived as dose per administration times the number of injections given during the study. Cumulative dose will be summarized using the number of subjects treated, mean, standard deviation, minimum, median, and maximum.

The Number of Study Drug Injections

The number of injections received at each scheduled time point by subject will be summarized with numbers.

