10.0 Efficacy Analysis**10.1 General Considerations**

This study is an open-label study without any comparator. The significant level is not defined, and descriptive statistics will be provided. These include the number of

observations, mean, standard deviation, minimum, median, and maximum for continuous variables; and number and percent for discrete variables. The exact 95% confidence intervals will be provided for the proportions. The analysis will be performed using SAS® (SAS Institute Inc., Cary, NC, USA). All efficacy analyses will be performed on the FAS.

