11.2 Analysis of Adverse Events

11.2.1 Treatment-Emergent Adverse Events

Treatment-emergent adverse events (TEAEs) are defined as events that begin or worsen either on or after the first dose day of the study medication and within 70 days after the last dose of the study medication. Treatment-emergent AEs will be summarized separately for the first half period (Week 0 to Week 24), the second half period (Week 24 to Week 52), and entire period (Week 0 to Week 52).

For the interim analysis at Week 24, treatment-emergent adverse events are defined as any event with an onset or worsening on or after the first dose of study drug and on or prior to the Week 24 dosing date for subjects who continued in the study after Week 24, and up to 70 days after the last dose of study drug for subjects who discontinued prior to Week 24 visit.

Treatment-emergent adverse events will be summarized and presented using primary Medical Dictionary for Regulatory Activities (MedDRA) system organ classes (SOCs) and preferred terms (PTs) according to the version of the MedDRA coding dictionary used for the study at the time of database lock. The actual version of the MedDRA coding dictionary used will be noted in the clinical study report. The system organ classes will be presented in alphabetical order and the preferred terms will be presented in alphabetical order within each system organ class.

For the Dose Escalation set, TEAEs will be reported before the date of dose escalation and also on or after the date of dose escalation, separately.

Adverse Event Overview

The number and percentage of subjects experiencing treatment-emergent adverse events will be summarized for the following adverse event categories.

- Any treatment-emergent adverse event

- Any treatment-emergent adverse event that was rated as possibly related to study drug by the investigator (Reasonable Possibility)
- Any treatment-emergent severe adverse event
- Any treatment-emergent serious adverse event
- Any treatment-emergent adverse event leading to discontinuation of study drug
- Any treatment-emergent serious adverse event that was rated as possibly related to study drug by the investigator (Reasonable Possibility)
- Any treatment-emergent adverse event leading to death
- Any treatment-emergent adverse event of special interest
- Any Deaths

Adverse Events by SOC and PT

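### The 95% intervals for mean change in vital signs and weight use the standard normal distribution at about 10 subjects, so at n = 10 they cover about 92%

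*SAP*

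**What the plan says.** SAP 11.4.1 covers the mean change from baseline to each post-baseline value, for every vital sign and for weight, in the Safety Dataset. These are to be summarised "using the descriptive statistics including 95% confidence interval based on standard normal distribution". SAP 11.4 introduces the list of variables with "The following vital signs are measured at the designated study visits" and names systolic and diastolic blood pressure, pulse, respiratory rate, body temperature and body weight.

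Three other places fix the setting:

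- SAP 4.3: "the target number of subjects is set 10 subjects".
- SAP 6.5: "In general, missing Baseline and safety data will not be imputed".
- SAP 10.1, for efficacy: "The exact 95% confidence intervals will be provided for the proportions".

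Neither document gives a known standard deviation for these changes or a t-based alternative.

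A secondary point concerns the adverse event rates per 100 patient-years in SAP 11.2.1. The numerator is the total count of treatment-emergent events, defined as starting on or after first dose "and within 70 days after the last dose of the study medication". The denominator is exposure, and SAP 9.1 says: "Duration of exposure is defined the number of days since first dose of study drug through the last dose date plus 14 days".

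**The concern.** The normal quantile is right for a mean when the standard deviation is known, or when n is large enough for the error in estimating it to be negligible. Neither holds here. The standard deviation comes from at most about 10 changes, and the number falls at any visit with missing data. Intervals built with 1.96 would be labelled 95% and be too narrow, so a reader would take mean changes in blood pressure, pulse or weight to be better determined than they are.

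For the adverse event rates, events may be counted for up to 70 days after last dose while person-time stops at 14 days. If so, the rate per 100 patient-years is overstated by any event that falls in the 56 days between.

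**Working it through.** **Inputs.** Confidence level 95%, so z = 1.960 (SAP 11.4.1). Planned n = 10 (SAP 4.3). The values n = 8 and n = 6 are my illustrations of visits with missing data. The documents give no dropout forecast; 6 is also the lower end of the sample-size range in SAP 4.3.

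**The nominal level.** With a known standard deviation, mean ± 1.96·σ/√n covers exactly 95%. With the sample standard deviation s and normally distributed changes, (mean − μ)/(s/√n) follows a t distribution on n − 1 degrees of freedom. The coverage of mean ± 1.96·s/√n is then P(|t(n−1)| ≤ 1.96), so the stated 95% is not reproduced.

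| n | Coverage with 1.96 | Simulated coverage | t quantile | z interval too narrow by (1 − 1.96/t) | t interval wider by (t/1.96 − 1) |
|---|---|---|---|---|---|
| 10 | 91.84% | 91.86% | 2.262 | 13.4% | 15.4% |
| 8 | 90.92% | 90.92% | 2.365 | 17.1% | 20.6% |
| 6 | 89.27% | 89.25% | 2.571 | 23.8% | 31.2% |

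The simulation used 400,000 normal samples for each n.

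**Shift in each limit.** Moving from z to t moves each limit by (2.262 − 1.960)/√10 ≈ 0.10 standard deviations at n = 10, and by (2.571 − 1.960)/√6 ≈ 0.25 at n = 6.

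**Number of outputs.** Six variables (SAP 11.4) at 14 post-baseline visits (SAP 6.4, Table 4) give 6 × 14 = 84 intervals. The expected number that miss the true mean change is:

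- at a true 95%: 84 × 0.05 = 4.2
- with 1.96 and n = 10 at every visit: 84 × 0.0816 = 6.9
- with 1.96 and n = 8 at every visit: 84 × 0.0908 = 7.6
- with 1.96 and n = 6 at every visit: 84 × 0.1073 = 9.0

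Expectations add even though the intervals are correlated.

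**Adverse event rates (secondary).** The last planned dose is at Week 50, Day 351. Exposure ends at 351 + 14 = Day 365, and the treatment-emergent window ends at 351 + 70 = Day 421. A subject whose last dose is at Week 16 (Day 113) contributes 127 exposure days and 183 event days. Suppose events are counted to 70 days at a constant rate on and off drug, in 10 subjects. The rate is then inflated by:

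- all complete: 4210/3650 = 1.15
- two stop at Week 16: (8 × 421 + 2 × 183)/(8 × 365 + 2 × 127) = 3734/3174 = 1.18
- five stop at Week 16: (5 × 421 + 5 × 183)/(5 × 365 + 5 × 127) = 3020/2460 = 1.23

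The extra time is 10 × 56 = 560 days in every case. If the off-drug rate is half the on-drug rate, the factor is 1 + 0.5 × 560/3650 = 1.08 when all complete and 1 + 0.5 × 560/2460 = 1.11 when five stop. With no off-drug events it is 1.00.

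At the Week 24 interim the windows agree for subjects still on study: "the Week 24 dosing date will be used instead of last dose plus 14 days only for ongoing subjects", and SAP 11.2.1 cuts their events at the same date. The question therefore concerns the final analysis and interim discontinuers.

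**The case against.** The strongest case is that this hardly matters. Protocol 8.1.2 and 8.1.5 promise only descriptive statistics for safety variables, and no decision rests on these intervals. SAP 6.0 reports mean and standard deviation and Protocol 8.1.2 adds the number of observations, so a reader could rebuild a t interval. All of that stands, and it is why the point is minor. It does not make the label correct.

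The wording may be shorthand for a normal-theory interval, with t intended. That is possible, but read literally it specifies 1.96, and a programmer has no other instruction. If t was meant, the same phrase needs correcting.

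The figures at n = 8 and n = 6 depend on missing data that the documents do not predict, and applying one low n to all 84 intervals is an upper illustration. This is accepted; the point is already present at n = 10 with nobody lost.

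Exact intervals for efficacy proportions do not oblige the SAP to use any particular method for safety means. This also stands in part. SAP 10.1 shows that small-sample methods were used elsewhere in the same plan, but the case against 1.96 does not depend on it.

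On the adverse event rates, SAP 11.2.1 also describes an overall summary period from Week 0 to Week 52. If that limits the numerator, events and exposure coincide for completers (both end at Day 365) and there is no inflation for them. The SAP does not say whether it does, so this is a request for clarification and not a demonstrated error.

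**Conclusion.** The concern holds, as a minor point. As written, SAP 11.4.1 gives intervals that cover about 92% and not 95% at the planned 10 subjects, and about 89% if only 6 contribute to a visit. This rests on approximately normal changes, a standard deviation estimated from the sample, and a literal reading of the SAP wording. The consequence is overstated precision in descriptive safety tables.

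The adverse event rate question is secondary and conditional. The overstatement ranges from none to about 1.15-fold if all complete, and up to 1.23-fold in the illustrated case of five early stops. Where it falls depends on which window applies, how many stop early and whether events continue off drug.

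**What to change.** In SAP 11.4.1, replace the reference to the standard normal distribution with the t distribution on n − 1 degrees of freedom, where n is the number of subjects with a change value at that visit. This is one phrase in the SAP and one line of programming. For roughly normal changes the intervals then carry their stated 95%; simulated coverage was 95.0% to 95.1% at n = 10, 8 and 6. The cost is the extra width shown in the last column of the table.

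In SAP 11.2.1, add a sentence that fixes one window for the adverse event rates: events to 14 days after last dose over exposure time, or events to 70 days after last dose over observation time, or both reported side by side. State also whether the overall-period tables include events that start after Week 52.

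Neither change affects data collection, sample size or the primary analysis.

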12.0 Summary of Changes

No major changes were made to the analysis plan. Minor correction are as follows.

12.1 Summary of Changes Between the Latest Version of Protocol and the Current SAP**12.2 Summary of Changes Between the Previous Version and the Current Version of the SAP**

- Corrected the information of protocol version and updated the SAP version in section 3.0.
- The sentence, This is the first version of SAP for Protocol M14-193., was removed.
- Add Efficacy Assessment Criteria table for clinical response in section 10.2 based on Administrative change 4.

